7 STATISTICAL ANALYSES

7.1 General

In substudy 1 and 2 we will perform a Mixed Effect Analysis. Intention to treat is used so that patients who do not show up for primary outcome will still be included.

In substudy 3 we will perform a paired t-test.

7.2 Statistical Analysis Plan

Statistical analysis will be undertaken using PRISM version 9.3.1. All analyses will be conducted on an intention-to-treat principle using all randomized participants in the groups they were originally randomized to. A blinded statistician will perform the data analysis. In the per-protocol analysis only patients complying at least 75% with the treatment protocol are included in the statistics.

A blinded statistician will perform the data analysis.

Demographic and anthropometric characteristics (gender, age, mass, height, body mass index, sporting activities and pain duration) will be determined at the baseline visit for each treatment group.

Statistical analyses will be conducted on all outcome measures at all timepoints. However, the primary end-point will be the total score of the VISA-A questionnaire at 3 and 6 months in substudy 1; VISA-A total score and pain-subscales at 6 months in substudy 2; and VISA-A total score at 6 and 12 months in substudy 3. Between-group comparisons of treatment effect for all primary and secondary outcomes, will be performed with a mixed effect analysis. To assess for inferiority and superiority, mean between-group differences and two-sided 95% confidence intervals will be calculated.

The ordinal scaled data of patients overall assessment of the treatment effect (Lickert score -5 to +5) will be analyzed with the same mixed effect analysis, if the data is found normally distributed.

The ordinal scaled data on satisfaction with the exercise program is analyzed with the same mixed effect analysis, if the data is found normally distributed.

The ordinal scaled data of grading the flow within the tendon into 4 categories will be calculated using non parametric statistics: Mann-Whitney U-tests.

Return to sport in percent of earlier sports activity will be compared using unpaired t-test if the data is normally distributed, otherwise non parametric analysis (Mann-Whitney) is performed.

In substudy 1 the survival rate in each exercise group is illustrated on a Kaplan-Meier plot and differences are calculated using Log rank test (Mantel-Cox test).

A two-sided P value of less than 0.05 will be considered to indicate statistical significance.

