In cases where the above treatment measures are ineffective, surgery may be considered. Surgery of midsection AT has been tried for many years. Traditionally with longitudinal incisions of the tendon in the thickened part, but in recent years mainly as a minor intervention with a removal of the peritendium around the tendon (tenolysis) – especially on the front of the tendon, where vascular ingrowth with nerve fibers is assumed to be a large part of the cause of the pain from the tendon. Ruergård A et al (2019) have indicated a success rate of 89% with painlessness and return to sports at the same level as before the Achilles problems. In addition to this study, there are only small retrospective series of the effect of tenolysis, and in all the studies it is unclear to what extent and how effectively conservative treatment has been tried.

The purpose of our study is to compare an app based daily home training with physiotherapist supervised slow heavy strength training combined with load reduction by abstaining from running and jumping activities. This will be interesting because app based training is less costly than physiotherapeutic guided training. In addition, we will compare 50 ml of HVI with CS with 2 ml of CS injection as a supplement to training, in those patients who do not achieve satisfactory results with training alone. Finally, patients with continued problems will be offered surgery with Achilles tenolysis in an open prospective study.

The study is based on the following hypotheses:

- 1) Treatment with an app based daily home workout is as effective as slow heavy strength training (non-inferiority study).
- 2) 50 ml HVI with CS is better than 2 ml CS injection in addition to continued training, in those patients who do not achieve satisfactory results with training alone (superiority study).

- 3) Surgery with surgical tenolysis results in a clinically relevant reduction of pain symptoms in patients without sufficient effect of structured and monitored conservative treatment (the above conservative regimen).

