5 SAMPLE SIZE AND POWER

Sub-study 1

The risk of finding a difference between groups, even if there really is none, is set at 5% (risk of type I error), while the risk of overlooking a difference between the groups that is actually present is set at 20% (type II error). All outcome parameters will be analyzed using Mixed Effect Analysis

Statistical Analysis Plan	Date: nov 27, 2022
Exercise/Injections/operation in Achilles midsubstance tendinopathy	
Bispebjerg Hospital	

with treatment regime (group) and time as main factor (GraphPad Prism version 9.3 for Windows, GraphPad Software, La Jolla California USA, www.graphpad.com). All analysis are performed as an intention-to-treat analysis. If a patient drops out due to no improvement or too much pain to continue exercise therapy, the missing data will still be included using the mixed effect analysis.

Q-Q plots will be visually examined prior to analysis to ensure that the assumption of normal distribution is not violated. Significance level is set to 0.05. We will also compare the “survival rate” in each training group, and compare the end result after training by performing per protocol analysis. Patients not complying at least 75% with the training protocol are not included in the per-protocol statistics.

The minimum relevant difference in VISA-A is set at 15. However, as a non-inferiority study, the difference is set to $15/2 = 7.5$. Based on other studies on pain intensity, we expect a mean baseline of 50 and an average improvement of 17. The standard deviation (SD) on the VISA-A measurements in these studies is 13. Power of 80% gives a sample size of 38 participants in each group. We plan to include 45 in each group in case of data loss and no-shows, for a total of 90 patients.

Sub-study 2:

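### Sub-study 1 is designed and sized as a non-inferiority study with a 7.5-point margin, but section 7.2 never compares the confidence interval with that margin, so no stated result establishes non-inferiority

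*SAP*

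**What the plan says.** The design is clear. Hypothesis 1 in section 1 reads "Treatment with an app based daily home workout is as effective as slow heavy strength training (non-inferiority study".

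Section 5, under Sub-study 1, gives the margin: "The minimum relevant difference in VISA-A is set at 15", and then "However, as a non-inferiority study, the difference is set to" 15/2 = 7.5. The other inputs follow: "The standard deviation (SD) on the VISA-A measurements in these studies is 13" and "Power of 80% gives a sample size of 38 participants in each group", raised to 45 per group for losses. The same section defines the 5% type I error as declaring a difference that does not exist, and the 20% type II error as missing one that does.

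Section 7.2 covers all between-group comparisons in one sentence: "To assess for inferiority and superiority, mean between-group differences and two-sided 95% confidence intervals will be calculated". It closes with "A two-sided P value of less than 0.05 will be considered to indicate statistical significance". The figure 7.5 does not appear in section 7, and neither does the term non-inferiority.

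**The concern.** A non-inferiority conclusion rejects the null hypothesis that the app is worse than HSR by the margin or more. Its type I error is accepting an app that is that much worse. Section 5 instead controls the error of a difference test, whose null is no difference at all. Section 7.2 supplies a threshold for that difference test and an interval with no margin attached. It does not say which contrast is formed, which limit matters, or what value the limit must clear.

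The analyst is left with a P value and an interval, but no written route from either to hypothesis 1. A P value of 0.05 or more could then pass as support for the app being as effective, although it may reflect only imprecision. The conclusion of sub-study 1 depends on which reading is taken, and the choice would be made after the data are seen.

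**Working it through.** **Inputs.** From section 5: margin 7.5, SD 13, power 80%, 38 per group, 45 with allowance for loss. From section 7.2: two-sided 95% interval and two-sided 0.05. Assumptions of this check: one time point, unadjusted two-sample comparison, contrast app minus HSR, so a negative value means the app is worse.

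**1. Reproduce the 38.** With a true difference of 0, n per group = 2 × 13² × (z_α + z_β)² / 7.5², where z_β = 0.842.
- One-sided 5% (z_α = 1.645): 2 × 169 × 2.487² / 56.25 = 37.2, rounded up to **38**. This matches.
- One-sided 2.5%, the level of a two-sided 95% interval (z_α = 1.960): 2 × 169 × 2.802² / 56.25 = 47.2, rounded up to 48. No match.
- Two-sided 5% test of a 15-point difference: 2 × 169 × 2.802² / 225 = 11.8, rounded up to 12. No match.

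The trial was therefore sized for a margin test, at one-sided 5%.

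**2. Precision.** SE = 13 × √(2/n). Half-width = t(0.975; 2n − 2) × SE.
- n = 45: SE = 2.74, half-width = 5.45.
- n = 38: SE = 2.98, half-width = 5.94.

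**3. Where the two readings disagree.** An estimate is non-significant if it lies above minus the half-width (and below plus the half-width). The lower limit clears -7.5 only if the estimate exceeds half-width − 7.5. Estimates between these two values are non-significant although the interval crosses -7.5:
- n = 45: from -5.45 to 5.45 − 7.5 = **-2.05**.
- n = 38: from -5.94 to 5.94 − 7.5 = **-1.56**.

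**4. Error when the app is truly 7.5 points worse** (non-central t, non-centrality 7.5/SE).

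| Analysed per arm | P ≥ 0.05 for the difference | Lower 95% limit above -7.5 |
|---|---|---|
| 45 | 22.8% | 2.5% |
| 38 | 30.1% | 2.5% |

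**5. When there is truly no difference, 45 per arm.** 95% of trials are non-significant, but only 77.2% meet the margin rule. The 2.5% with a significant deficit fail both readings, so about 100 − 77.2 − 2.5 = 20.3% are non-significant without showing non-inferiority.

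**6. Power of the margin rule with a 95% interval** (t distribution, true difference 0): 70% at 38 per arm and 77% at 45. On the normal approximation of step 1, 80% needs 48 analysed per arm.

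**The case against.** The strongest reply is that the parts of a proper rule are all in this SAP: the design in section 1, the margin in section 5 and a two-sided 95% interval in section 7.2. The pair of terms in 7.2 mirrors the two labelled hypotheses in section 1, so *inferiority* is quite possibly a slip for *non-inferiority*. The 0.05 sentence is a general closing definition for every test in three sub-studies, not one assigned to hypothesis 1. All of this stands, and it makes the point a gap in wording rather than a missing analysis. It does not close the gap. The contrast, the limit and the margin still have to be supplied by the reader, and the sample size points to one-sided 5% while 7.2 points to 2.5%.

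Some stronger readings are tempting but not supported:
- *The plan will treat non-significance as proof that the app is as effective.* No section says so. The rates of 23% and 30% are conditional on that reading.
- *A small significant deficit inside the margin would wrongly count against the app.* For both to occur the half-width must be under 7.5/2 = 3.75. With SD 13 and 45 per arm it is 5.45. It would take about 94 per arm, or an SD below about 3.75 / (1.987 × 0.2108) = 8.95 at 45 per arm.
- *Transfers to sub-study 2 would leave about 20 per arm and push the error far higher.* Section 5 expects about 50 patients to continue in sub-study 2, but section 3 lets them leave sub-study 1 at any time from 1 to 12 months. Sections 5 and 7 keep all randomised patients in the mixed effect analysis, so a comparison of completers alone is not planned.
- *The app passes unless its whole interval lies below -7.5.* The SAP states no such rule.

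**Conclusion.** The point holds as a defect in the written decision rule. Sub-study 1 is sized for a margin test that section 7.2 does not specify, and section 5 describes the type I error of a different test. If a non-significant difference were read as showing the app to be as effective, an app truly 7.5 points worse would be accepted in about 23% of trials with 45 per arm and 30% with 38, against 2.5% under the margin rule.

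These figures rest on SD 13, one time point and an unadjusted comparison. A mixed model that uses earlier measurements could have a smaller residual SD, for which the SAP gives no figure. That would change the rates but not the absence of a rule. The documents show that the misreading is left open, not that it is planned.

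**What to change.** In section 7.2, add for sub-study 1:

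> For sub-study 1, non-inferiority of app training to HSR is concluded at a primary time point if the lower bound of the two-sided 95% CI for the mean difference in VISA-A total (app minus HSR) lies above -7.5. A P value of 0.05 or more for the difference is not evidence of non-inferiority.

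Then:
- Change *inferiority and superiority* to *non-inferiority (sub-study 1) and superiority (sub-study 2)*.
- State that the 0.05 threshold does not decide the sub-study 1 non-inferiority question. It stays for all other tests, including the paired t-test in sub-study 3.
- Reword the type I error for sub-study 1 in section 5 as the risk of concluding non-inferiority when the app is worse by 7.5 points or more.
- Because 3 and 6 months are both primary, say how the two results combine into one conclusion.
- Restate the power under the 95% rule: about 70% with 38 and 77% with 45 analysed per arm.

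The interval is already planned, so no new analysis or data are needed, and section 7.4 records that no analysis had begun at signing. There are two costs. Some non-significant results will have to be reported as non-inferiority not shown, and the SAP must acknowledge power below the stated 80%.

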7.3 Interim analysis and early stopping rules

Anecdotally, an increased risk of tendon rupture have been reported. To account for this, we have introduced an early stopping rule if the rate of Achilles tendon ruptures exceeds 2 ruptures.

7.4 Timing of analyses

When this statistical analysis plan was signed, recruitment to the main trial was started, but no analysis had been initiated.

SUB-STUDY 1								
	Enrolment	Allocation						
TIMEPOINT	april 2022 – end 2024	april 2022 – end 2024	Month 1	Month 2	Month 3	Month 6	Month 9 Jan 2023 end 2025	Month 12 April 2023 end 2025
ENROLMENT:								
Eligibility screen	X	X						
Informed consent		X						
Allocation		X						
INTERVENTIONS:								
Intervention group 1			←————→					
Intervention group 2			←————→					
ASSESSMENTS:								
Diagnosis		X						
VISA-A		X	X	X	X	X	X	X
Morning pain [VAS]		X	X	X	X	X	X	X
Pain after activity [VAS]		X	X	X	X	X	X	X
Return to usual sports participation						X	X	X
Satisfaction with result of treatment			X	X	X	X	X	X
Patient diary for reporting compliance and adverse events			←————→					
Ultrasound examinations		X	x	x	X	X	X	X
Demographics		X						

Table 1: SPIRIT figure. Schedule of enrolment, interventions and assessments

SUB-STUDY 2								
	Enrolment	Allocation						
TIMEPOINT	July 2022 – July 2024	July 2022 – July 2024	Month 1	Month 2	Month 3	Month 6	Month 9 Jan 2023 end 2025	Month 12 April 2023 end 2025
ENROLMENT:								
Eligibility screen	X	X						
Informed consent		X						
Allocation		X						
INTERVENTIONS:								
Exercise group 3+4			←————→					
Exercise group 5+6			←————→					
ASSESSMENTS:								
Diagnosis		X						
VISA-A		X	X	X	X	X	X	X
Morning pain [VAS]		X	X	X	X	X	X	X
Pain after activity [VAS]		X	X	X	X	X	X	X
Return to usual sports participation						X	X	X
Satisfaction with result of treatment			X	X	X	X	X	X
Patient diary for reporting compliance and adverse events			←————→					
Ultrasound examinations		X	x	x	X	X	X	X
Demographics		X						

SUB-STUDY 3					
	Enrolment	Allocation			
TIMEPOINT	End 2022 – end 2025	End 2022 – end 2025	Month 3	Month 6	Month 12 End 2023 – end 2026
ENROLMENT:					
Eligibility screen	X	X			
Informed consent		X			
Allocation		X			
INTERVENTIONS:					
operation		x			
ASSESSMENTS:					
Diagnosis		X			
VISA-A		X	X	X	X
Morning pain [VAS]		X	X	X	X
Pain after activity [VAS]		X	X	X	X
Return to usual sports participation				X	X
Satisfaction with result of treatment			X	X	X
Patient diary for reporting compliance and adverse events					
Ultrasound examinations		X	X	X	X
Demographics		X			

8 DEVIATIONS FROM THE PROTOCOL

The following details in this SAP represents deviations from protocol version 3

Header in protocol	Change	Reason
